View: SF - Research Description

Research Description

1. Describe the study hypothesis and/or research questions. Use lay language whenever possible.

The hypothesis of this prospective single bilind randomized trial is that general anesthesia with laryngeal mark airway is non-inferior in length of procedure to endotracheal tube for patients undergoing abiation for atrial fibrillation.

Secondary hypothesis:
The secondary hypothesis is that general anesthesia with LMA is superior or non-inferior to endotracheal tube in duration of fluoroscopy, post procedure side effects, patient satisfaction and recurrence of PAF.

Describe the study's specific aims or goals. Use lay language whenever possible.
 Study goal is to determine if the use of laryngeal mask airways in abiation of atrial fibrillation is non-inferior to endotracheal tube in terms of procedure length.

3. Describe the study's background and significance, including citations, or upload a citation list in document upload. Use lay

language whenever possible.

In recent years it has been shown that catheter abiation of symptomatic atrial fibrillation (PAF) is superior to antiarmythmic drug therapy with regards to effectiveness and clinical outcomes. 1 Atrial fibrillation is the most common cardiac arrhythmia, with high rates of concomitant heart failure, stroke and mortality.2,3 During an abiation procedure, a patient can be managed with intravenous sedation or General Anesthesia. Within this setting, General anesthesia is associated with improved procedure time and cure rate compared to

Airway management during GA can be achieved through a LMA or an ETT. The use of LMA compared to ETT has been shown in different surgical populations to decrease procedure and recovery time, improve hemodynamic stability and reduce anesthetic requirements.5,6,7 it has also shown to decrease airway complications, and postoperative nausea/vomiting which are important factors that affect overall patient satisfaction.8,9,10,11,12

Although general anesthesia in electrophysiology procedures is associated with a higher cure rate, there have been reports of increased airway trauma.13 Additionally, it is believed that voiatile anesthetics may be associated with increased ventricular action potential duration as well as prolonged QT interval.14,15 The increased usage of opioids during general anesthesia is also thought to interfere with electrophysiology studies by affecting vagal tone.16

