At VCU Health system, Anesthesiologists have been successfully using LMA (General Anesthesia) for ablation in PAF in eligible patients for over five years. The investigators are proposing a randomized, single blind study to evaluate the use of LMA versus ETT in this patient population. A concurrent retrospective study will be conducted to evaluate the last two years data of outcomes in this patient population at VCU. The investigators wish to do a prospective study to reduce bias, as the patients who have greater comorbidities are more likely to have ETT for an esthesia, and we believe this will skew the retrospective data when it is collected. The LMA used at VCU Health are LMA Supreme (Teleflex Medicals, Ireland). The study is designed as a non-inferiority study with a primary outcome of procedure length.

Secondary outcomes will include flouroscopy duration, total anesthesia time, total intra- and post- procedure opioids and ionotropes/pressors/chronotropes, patient satisfaction, PAF recurrence.

Briefly describe the study design, including all interventions or interactions with research participants and access to identifiable data. Use lay language whenever possible.

This will be a prospective, randomized single blind study comparing the use of general anesthesia with endotracheal tube versus laryngeal mask airway in patients undergoing abiation for paroxysmal atrial fibrillation. Patients will be consented the morning of the procedure and will be conducted only by study personnel. All patient identifiers will be stored in a separate, password protected document from data set. Patients will be randomized, data collected and stored in the secure REDCAP database. REDCap database randomization software will be used to randomize patients into one of the two study groups. Patients will be randomized after they sign informed consent the morning of the procedure. Randomization will be done by study personnel using REDCap and verbally conveyed to anesthesia provider that morning of procedure. The minimum necessary study personnel will have access to patient identifiers.

Power analysis: Estimated mean procedure time 3 hours, range 1.5-4.5 hours, standard deviation 0.9, n = 82 to detect 0.5 hour margin of non-inferiority between the two groups. Including 5% drop-outs, final n=87. Goal enrollment 44 patients per group.

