		ocedure pressor/lonotrope/chronotrope requirements: total measured amounts of all pressors/lonotropes and chronotropes stered intraoperatively
	Electro proced	ophysiology Parameters: size of left abrium (mm), left ventricular ejection fraction; duration of paroxysmal abrial fibrillation prior to ure
		trauma: Any noted trauma in the anesthesia or post-procedure notes, including damage to lips/leeth, laryngospasm, need for ation post procedure
	Post-p	rocedure nausea: Measured by number of doses of antiemetics given in the post-procedure time period.
	Post-p	rocedure emesis: Measured by number of times patient has emesis during post-procedure time period.
	proced	ibriliation recurrence: defined as recurrence of paroxysmal atrial fibriliation recurring at any time after 6 weeks past the day of lure. As standard of care these patients are followed up with Holter monitoring for a period of 6 months. Holter monitoring will be or 48 hour time periods immediately post-procedure, 2 weeks, 6 weeks, 4 months and 6 months post procedure as is standard of
	Aspira	tion events: aspiration events as noted in the anesthesia, PACU and post procedure notes would be documented.
		t Satisfaction: patients will be given an survey by study personnel prior to discharge from the hospital; survey will be conducted in by study personnel
	Cost A	nalysis: an analysis of cost to patient as well as overall hospital costs will be conducted
2	Informa	ribe the source(s) of the protected health information: ation will be collected both by reviewing data from the medical record of VCU Health, Cemer as well as by in person surveys cled prior to hospital discharge.
3.	PHI co	ain how the PHI collected or used in this research is the minimum necessary to accomplish this research: illected is minimum necessary to determine our primary and secondary outcomes in determining if the use of LMA is non-inferior to r abilation for atrial fibriliation.
4	. * Selec	ct all pathways this research will employ to use or access PHI:
		- Marine a Robert
		e-Identified Data
	u	mited Data Set
	_ W	laiver of Authorization
	₽ P	artial Walver of Authorization
	₹ \$	igned Authorization Combined with Consent Form
	S	gned Authorization as Stand-Alone Form

De-Identified Data	
Limited Data Set	
Waiver of Authorization	
✓ Partial Waiver of Authorization	
Signed Authorization as Stand-Alone Form	

View: SF - Partial Walver of Authorization

Partial Waiver of Authorization

ID: HM20007902

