4. If applicable, upload a Co	ost Analysis form here:
: HM20007902	View: SF - Standard of Care Vs. Research Costs

Standard of Care Vs. Research Costs

1. *Describe any procedures, therapy, lab work, x-rays, drugs, or devices, etc that are considered standard of care and will be charged to the participant or their insurance:

All associated procedures involving anesthesia, abiation, hospitalization, post procedure holter monitors and post procedure office visits are considered standard of care and will be charged to participant and their insurance.

2. Describe the process to determine whether participants' insurance will cover the expenses: Patients will have the procedure and all associated expenses submitted to insurance as standard of care.

ID: HM20007902

View: SF - Compensation

Compensation

- Describe any compensation that will be provided including:
 Items such as parking/transportation

 - total monetary amount
 - type (e.g., gift card, cash, check, merchandise, drawing, extra class credit)
 how it will be disbursed:

No compensation.

2. If compensation will be pro-rated, explain the payment schedule:

ID: HM20007902

View: SF - Risks, Discomforts, Potential Harms and Benefits

Risks, Discomforts, Potential Harms and Benefits

- Describe the risks to participants associated with this study:

 physical, psychological, social, legal, financial, and other risks
 - seriousness of given risks
 - probability or likelihood of given risks

The risks of LMA airway management in atrial fibrillation abiation are: gastric aspiration, intraoral trauma, intraoral nerve paisies, largynospasm, incorrect placement, need for conversion to ETT, sore throat, pulmonary edema, bronchoconstriction

The risks of ETT airway management in atrial fibriliation abiation are: oral injury, dental injury, incorrect placement, hoarseness, sore throat, laryngospasm, laryngeal injury, difficulty swallowing.

There is a potential risk of loss of condifentiality.

2. Describe how the risks / harms will be minimized:

Risks/harms will be minimized as patient data will be carefully managed and accessible by minimum necessary study personnel. Risks are minimized as both groups will have anesthetic plans that have been proven safe and standard of care in a wide variety of clinical

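### The side-effect hypothesis is only partly covered by the defined data: throat symptoms have no named field, and nausea is recorded only as antiemetic doses over an open-ended period

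*Combined protocol and SAP*

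**What the plan says.** All references are to the Combined protocol and SAP.

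- **Hypothesis** (SF - Research Description, item 1). The LMA is expected to be "superior or non-inferior to endotracheal tube in duration of fluoroscopy, post procedure side effects, patient satisfaction and recurrence of PAF". No component of side effects, margin or test is named.
- **Outcome list** (SF - Research Description, end of the background). "Secondary outcomes will include flouroscopy duration, total anesthesia time, total intra- and post- procedure opioids and ionotropes/pressors/chronotropes, patient satisfaction, PAF recurrence". No side effect appears.
- **Device risks** (SF - Risks, Discomforts, Potential Harms and Benefits, item 1). The ETT risks include "hoarseness, sore throat, laryngospasm, laryngeal injury, difficulty swallowing". The LMA risks also include sore throat.
- **Data fields** (SF - HIPAA, item 1). Airway trauma is "Any noted trauma in the anesthesia or post-procedure notes, including damage to lips/leeth, laryngospasm", followed by a post-procedure need whose wording is damaged in the text. Nausea is "Measured by number of doses of antiemetics given in the post-procedure time period". Emesis is a count of episodes, and aspiration is taken from the notes.
- **Survey** (same item). Study personnel survey patients in person before discharge. The survey is described only as measuring satisfaction, and its items are not in the text.
- **Medication** (SF - Research Description, study design). Anesthetic drugs follow usual care; enrollment dictates none of them.

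**The concern.** Items 11 and 12 of the risks and benefits section offer fewer side effects as a possible gain for participants, and better knowledge of side effects as a scientific gain. A conclusion about side effects is therefore an intended product of the trial. Because the outcome list names none, the only working definitions are the data fields.

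Those fields hold events that staff write down and doses that staff give. They do not name the throat symptoms that a patient feels and that the plan itself attributes to the devices. Nausea is also a felt symptom, and here it is replaced by a treatment decision. If the data list is followed literally, a statement that one airway has fewer side effects could leave throat symptoms out and could mix nausea with prescribing and length of observation. Symptoms that nobody asks about before discharge cannot be reliably recovered from charts later.

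**Working it through.** The plan gives no figure for any side-effect outcome, so there is none to reproduce. Its sample size (82, or 87 with 5% drop-out) concerns procedure time only. The check is a comparison of the sections.

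**Step 1. Hypothesis against outcome list.** The hypothesis names fluoroscopy duration, side effects, satisfaction and recurrence. The outcome list has fluoroscopy duration, satisfaction and recurrence, and adds anesthesia time and drug totals. Side effects are the one element of the hypothesis with no counterpart.

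**Step 2. Listed ETT risks against data fields.**

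| ETT risk | Field |
|---|---|
| Laryngospasm | Named under airway trauma |
| Oral, dental and laryngeal injury | Airway trauma, if noted in the record |
| Incorrect placement | None named, but this is a placement event and not a post-procedure side effect |
| Sore throat, hoarseness, difficulty swallowing | None |

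The count is 1 + 3 + 1 + 3 = 8, so three of eight are throat symptoms without a field. Sore throat has none for the LMA either. The trauma field covers charted injury and is not a symptom measure. Some other LMA risks, such as pulmonary edema, also lack a named field. I do not press those, since a risk disclosure need not become an outcome list.

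**Step 3. What the nausea field counts.** Three things besides nausea can move the dose count:

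- *Treatment.* Nausea that is not treated scores zero. A dose given by routine scores the same as one given for symptoms.
- *Prophylaxis.* The data list records intra-procedure opioids, anesthetics and pressors, but not antiemetics. Medication is not standardised, so differences in intra-procedure antiemetics could not be seen or allowed for.
- *Length of observation.* The period has a start but no stated end. As a simplification, let doses be given at a constant rate r per hour in both arms, with observation times T_LMA and T_ETT. Expected doses are r × T_LMA and r × T_ETT, and their ratio is T_LMA / T_ETT whatever the value of r. With identical nausea, an observation time 10% shorter (an assumed figure) would give 10% fewer doses. The background says the LMA has shortened recovery in other surgical populations, and the plan records time to discharge from PACU. If stay differs by arm and the count follows the stay, the proxy would favor the arm with the shorter stay.

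**Step 4. Who supplies the data.** The anesthesia provider is told the allocation, and trauma and aspiration are taken partly from anesthesia notes. The trial is called single blind without saying who is blinded; the patient is the likely party. Study personnel perform the randomization and also give the survey, so the interviewer may know the device.

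**The case against.** The strongest reply is that the plan does measure the differences it expects. The only side-effect advantage stated in the background is that the LMA is said to "decrease airway complications, and postoperative nausea/vomiting which are important factors that affect overall patient satisfaction", and both parts have fields. Emesis, laryngospasm, lip or tooth damage and aspiration are recorded as events, and only nausea is a proxy. Sore throat is listed as a risk of both devices, so the plan does not present it as a difference between arms. This stands. A reader might infer from the missing fields that differences in side effects will not be measured at all. The documents do not support that: several are recorded directly and nausea is recorded indirectly.

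A second reply concerns the survey. A reader might infer that patients are never asked about their throat or about nausea. The items are not visible, and their absence from the text is not a fault in the plan. If the survey already asks, what remains is that the answers are not listed as outcomes. This also stands.

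Third, it is tempting to state how much power is lost. That would need symptom rates and an accuracy for the antiemetic proxy, and the documents give neither. I therefore offer no such figure.

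Fourth, patient report is not automatically unbiased when the interviewer may know the allocation. That is correct, and the fix takes account of it.

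None of these replies supplies a named outcome for throat symptoms, an end to the nausea period, or a side effect in the list of secondary outcomes.

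**Conclusion.** The concern holds in a limited form. Side effects are hypothesised on but absent from the secondary outcome list. Three patient-felt throat symptoms named as device risks have no defined field. Nausea is defined only by antiemetic doses over a period with no stated end, without a record of intra-procedure antiemetics. The side-effect hypothesis is thus partly covered by the defined data.

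The size is modest: it affects one part of a secondary hypothesis and leaves the primary outcome, the sample size and the non-inferiority conclusion untouched. The textual findings need no assumption. The distortion from length of stay is conditional: it arises only if the count follows the stay and stay differs by arm, and neither is established for this population. The survey's content is unknown and could reduce the point to one of outcome listing. The change is still worth making, because it is cheap and replaces a proxy with a direct measure.

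**What to change.** - Add patient-reported sore throat, hoarseness, difficulty swallowing and nausea to the existing pre-discharge survey, with one scale each covering the time since waking. If the survey already asks these, list them as outcomes.
- Where possible, have the survey given by existing study personnel who do not know the allocation.
- Name the four items as secondary side-effect outcomes alongside emesis, airway trauma and aspiration, not in place of them, so that the outcome list matches the hypothesis.
- Keep the antiemetic dose count as supporting data. Count it in a fixed post-procedure window, and record intra-procedure antiemetics from the anesthesia record.

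The cost is about one more minute per patient, one extra chart field and a few more secondary comparisons, to be reported as exploratory. Treatment, visits and sample size do not change.

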See 949	Use of Internet for Data Collection Registries/Repositories (Includes Accessing, Contributing or Creating) None of the Above Rect all Identifiers that will be collected as part of this study (Including for recruitment, data gathering, data analysis, etc. in if the data will eventually be anonymized: Names Geographic Locators Below State Level Social Security Numbers Dates (year alone is not an identifier) Ages >89 Phone Numbers F-acsimile Numbers E-mail Addresses Medical Record Numbers Blometric Identifiers Web URLs IP Addresses Account Numbers Health Plan Numbers Full Face Photos or Comparable Images License/Certification Numbers Vehicle ID Numbers

- 4. "Will participants be able to withdraw their data (paper, electronic, or specimens) from the study if they no longer wish to participate:

	Ye No.	
5.	Patient hospita	above, describe how participants will be able to withdraw their data: ts will be given a copy of consent form with contact information of study PI's and will be able to withdraw after discharge from the al by contacting those individuals. During hospital stay the care teams will have contact information for study personnel in case a wishes to withdraw during their hospitalization.
ID: HN	M20007	902 View: SF - HIPAA
HIP	PAA	
1.		ribe the protected health information that will be obtained or used in this research: ollection:
	Demog	graphics: age, race, comorbidities (diabetes, hypertension, coronary artery disease), weight, and height
	Proced	fure time: Will be measured as time from start of procedure to end of procedure, as recorded in minutes
	Fluoro	scopy time: As measured and reported by electrophysiology and radiology notes, recorded in minutes
		nesthesia time: Total anesthesia time as measured in minutes and recorded in the anesthesia record, from anesthesia start time to esia stop time
	Time to	o discharge from PACU: time from arrival to PACU until discharge from anesthesia care
		ntra-procedure opioids: Measured in total amount of opioids required during procedure, if different opioids used will convert to oral ine equivalents
	Anesth	etic Requirements: average end tidal volatile anesthetics, average amount of intravenous anesthetics
		perative hemodynamics: average heart rate, maximum heart rate, minimum heart rate, average MAP, minimum systolic blood re, maximum systolic heart rate, minimum diastolic blood pressure, maximum diastolic blood pressure

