Study Population 1. Provide the total number of participants you expect to enroll in this study under the VCU IRB: 2. If this is a multi-Center Project, what is the total anticipated number of subjects across all sites: 3. * Provide justification for the sample size: Power analysis: Estimated mean procedure time 3 hours, range 1.5-4.5 hours, standard deviation 0.9, n = 82 to detect 0.5 hour margin of non-inferiority between the two groups. Including 5% drop-outs, final n=87. Goal enrollment 44 patients per group 4. * List the study inclusion criteria: Patients undergoing primary abilation for paroxysmal atrial fibrillation - Able to obtain consent in English language 5. * List the study exclusion criteria: - Patients <18 years old Patients undergoing abiation for arrhythmias other than paroxysmai atrial fibrillation American Society of Anesthesiologist physical status of 4 or greater Patients undergoing repeat abiation - Pregnancy Prisoners - Patients unable to give their own consent - Patients having trans esophageal echo on the same day - Patients unable to give consent in English language - Patients will also be excluded if the attending anesthesiologist determines that they would not be suitable candidates for intubation with either method (ETT tube or LMA mask). - Patients with severed gastroesophageal reflux disease - Patients with high risk of aspiration 6. * Check all participant groups that are likely to be involved in this study. If it is possible that a regulated vulnerable population (children, pregnant women, prisoners) COULD BE involved in the study, be sure to check them: Healthy Volunteers Children Emandpated Minors Pregnant Women Fetuses, Neonates, Fetal Material or In-Vitro Fertilization Decisionally Impaired Adults When cancer is integral to the research - cancer Patients, Family Members, Healthcare Providers or Prevention VCU Health System Patients ■ Non-VCU Patients ■ VCU/VCUHS Employees Individuals with Limited English Proficiency Active Military Personnel When researching in a K-12 environment - populations Within School Districts or Other Learning Environments 7. If you are either targeting, or excluding, a particular segment of the population / community, provide a description of the group/organization/community and provide a rationale: Patients who are unable to consent in english language are being excluded as the investigators feel that it would be difficult to uniformly obtain informed consent and collect dta in this patint population. 8. * Select the age range(s) of the participants who may be involved in this study: < 1 Year
 1 - 6 Years 7 - 12 Years 13 - 17 Years √ 18 - 20 Years 21 - 65 Years > 65 Years View: SF - Potential Subject Identification and Recruitment ID: HM20007902 Potential Subject Identification and Recruitment 1. * Choose all recruitment methods that may be used:

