- If the disclosure of any of the information obtained during the study would place the individual at risk for harm (legal, reputation, emotional etc.) and the information will be recorded so that the individual could be identified, explain the protections that will be put in place to decrease the risk of disclosure:
- 4. * The Code of Virginia requires that most medical personnel and all employees of institutions of higher education report suspected child/elder abuse or neglect. Is it likely investigators could discover information that would require mandatory reporting by the investigators or staff:
 - Yes
 - No
- 5. Is it likely investigators could discover a participant's previously unknown condition (eg disease, suicidal thoughts, wrong paternity) or if a participant is engaging in illegal activities:
 - Yes
 - No
- 6. If yes, explain how and when such a discovery will be handled:
- 7. Describe any potential risks or harms to a community or a specific population based on study findings: There is minimal to no risk or harms to a community or specific population based on study findings.
- Pescribe criteria for withdrawing an individual participant from the study; such as safety or toxicity concerns, emotional distress, inability to comply with the protocol, etc.:

Participants will be withdrawn from the study if they are converted from their initial randomization. They will also be withdrawn if they request to be removed from study. Patients who do not complete all the post discharge holter monitor evaluations will be kept in the study, and the missed data fields will not be evaluated for that specific patients

- Summarize any pre-specified criteria for stopping or changing the study protocol due to safety concerns:
 No specified criteria for stopping or changing study protocol for safety concerns.
- 10. Where appropriate, discuss provisions for ensuring necessary medical, professional, or psychological intervention in the event of adverse events to the subjects:
- 11. Describe any potential for direct benefits to participants in this study: Participants in this study have potential for benefits of possibly fewer side effects, while also having a similar outcome with regards to

12. * Describe the scientific benefit or importance of the knowledge to be gained: The scientific benefit of knowing if the use of LMA is associated with similar (non-inferior) outcome in term of procedure length and

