determining if the side effects and patient satisfaction are superior could improve the anesthetic care of patients undergoing abiation of

- 13. If applicable, describe alternatives (research or non-research) that are available to potential participants if they choose not to participate in this study:
- 14. Indicate if this study will have a Data Safety Monitoring Board (DSMB) or a Data Safety Monitoring Plan (DSMP): [Required for all Full Review studies)

DSMB Review Required
✓ DSMP Required
Not Required

ID: HM20007902

View: SF - DSMP Details

DSMP Details

1. Describe your Data Safety Monitoring Plan for monitoring the data collected to ensure the safety of participants. Data collection will be done in a timely manner, with initial data input within a week of each visit. After the first 25 patients are enrolled an Interim analysis of primary outcomes as well as adverse outcomes will be done to determine if there is an association between either group and increased incidence of adverse outcomes. If an association is seen the IRB will be notified and the project design reevaluated.

View: SF - Consent Qualifiers ID: HM20007902

Consent Qualifiers

- 1. Are you submitting your study as exempt and therefore no consent is required:

No

ID: HM20007902

View: SF - Consent Groups

Consent Groups

1. " List all consent groups:

Group	Types	Waivers	Roles	Roles Consent	Coercion	Decision	Status Change
				Other			Onlang
Qualified Patients	Consent by	Walvers	Principal Investigator	Consent will be obtained in the	approached by study personnel and given facts of r study, no coercion will be utilized to encourage	e Patients will be y given from time approached by study personnel unti medications which may after decision making ability are given. Approximately 30 minutes to 1 hour	
	Participant	Requested	Co/Sub- Investigator	preoperative holding s area prior to procedure. Consent			ı
			Research Coordinator	will be obtained prior to patient receiving			
			Research Assistant	any medications which would potentially interfere			
			Trainee/Student			prior to procedure start.	
Patient Screening	None of the Above (select	Walver of Some or	Principal Investigator	No consent will be obtained	No consent will be obtained	No consent will be obatined	
	walver below)	All Elements of Consent	Co/Sub- Investigator				
		or consent	Research Coordinator				
			Trainee/Student				

2. Upload any consent / assent documents:

ID: HM20007902

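### Patients converted from the assigned airway are withdrawn after randomisation and nothing keeps them in the primary comparison; the resulting bias probably arises mainly in the LMA arm, with sign and size not identified

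*Combined protocol and SAP*

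**What the plan says.** The rule is in Risks, Discomforts, Potential Harms and Benefits, item 8 (criteria for withdrawing a participant): "Participants will be withdrawn from the study if they are converted from their initial randomization". Participants who ask to leave are also withdrawn. By contrast, the same item says that patients with incomplete Holter follow-up "will be kept in the study, and the missed data fields will not be evaluated".

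Other relevant places:

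- **Same section, item 1.** The LMA risk list includes "incorrect placement, need for conversion to ETT, sore throat". The ETT list has no conversion item.
- **HIPAA, item 1.** Procedure time is defined as follows: "Will be measured as time from start of procedure to end of procedure, as recorded in minutes". Conversion is not among the data items listed there.
- **Data Collection Details.** The form asks: "Will participants be able to withdraw their data (paper, electronic, or specimens) from the study if they no longer wish to participate". The answer covers patients who choose to leave. It does not cover patients withdrawn because of conversion.
- **Research Description, item 4.** Randomisation follows consent on the morning of the procedure, so conversion happens after randomisation. The power statement allows 5% for drop-outs and does not say whether conversions count.

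No section in the available text defines an analysis set or says that a converted patient's procedure time is still analysed.

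**The concern.** The hypothesis in Research Description, item 1, concerns general anesthesia with LMA. On a strategy reading, an LMA that has to be changed to an ETT is part of what is being tested. If those patients leave the comparison, the LMA arm is reduced to patients in whom the LMA worked while the ETT arm stays close to complete. The protection of randomisation is then lost for the primary endpoint.

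At stake is a non-inferiority conclusion that could come out too easily or too rarely, depending on how long converted cases run. Secondary outcomes could suffer too. On satisfaction, "patients will be given an survey by study personnel prior to discharge from the hospital", and a withdrawn patient may not receive it. Because conversion is not a listed data item, it might also not be reported by arm.

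**Working it through.** **1. The plan's sample size.** Inputs from Research Description, item 4, and Study Population, item 3: SD 0.9 h, margin 0.5 h, n = 82, 5% drop-out, final n = 87, 44 per group. Alpha and power are not stated.

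Per arm, n = 2 × [SD × (z_alpha + z_power) / margin]². With one-sided 5% and 80% power:

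2 × [0.9 × (1.6449 + 0.8416) / 0.5]² = 40.06, rounded up to 41 per arm, or 82 in total.

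82 / 0.95 = 86.3, rounded up to 87. Both figures reproduce. One-sided 2.5% with 80% power would give 102, so one-sided 5% is used below as an inferred value.

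**2. Form of the bias.** Let c be the share of LMA patients converted, and D the mean procedure time of converted minus unconverted LMA patients. The all-randomised LMA mean is the unconverted mean plus c × D. Dropping converted patients therefore shifts the LMA minus ETT difference by **-c × D**.

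- D > 0 (converted cases run longer): the shift favours LMA.
- D < 0 (for example, ETT-like times when LMA is slower): the shift goes against LMA.
- D = 0: no shift. This is possible if conversion occurs before the procedure clock starts.
- Equal conversion in both arms with the same D: the shifts cancel.

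**3. Size under assumed values.** The documents give neither c nor D. Assumed: c = 2% or 5%, D from -0.5 to +1.5 h, conversion in LMA only, 44 per arm, SD 0.9 h, and a true all-randomised difference of exactly 0.5 h. The table gives the simulated chance of wrongly declaring non-inferiority when converted patients are dropped (200,000 trials per cell, pooled t upper bound against 0.5 h).

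| D (h) | -0.5 | -0.25 | 0 | +0.25 | +0.5 | +1.0 | +1.5 |
|---|---|---|---|---|---|---|---|
| c = 2% | 4.5% | 4.6% | 5.0% | 5.2% | 5.6% | 6.1% | 6.8% |
| c = 5% | 3.8% | 4.4% | 4.9% | 5.7% | 6.4% | 8.2% | 10.3% |

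With everyone kept, the error is 4.8–5.2%. With equal conversion in both arms, dropping converted patients gives 4.9–5.1%. At one-sided 2.5%, the ranges are 2.2–3.6% (c = 2%) and 1.8–5.8% (c = 5%).

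Closed-form check: error = 1 - Phi(1.645 - c × D / SE), with SE = 0.9 × sqrt(1/44 + 1/(44(1 - c))). For c = 5%, D = +1 h: SE = 0.9 × sqrt(1/44 + 1/41.8) = 0.194, and 0.05 / 0.194 = 0.257. The error is 1 - Phi(1.388) = 8.3%, against 8.2% simulated.

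**4. In minutes.** At c = 5%, D = +1.5 h moves the estimate 0.05 × 1.5 × 60 = 4.5 minutes toward LMA. D = -0.5 h moves it 0.05 × 0.5 × 60 = 1.5 minutes against LMA. The margin is 30 minutes.

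**5. A limit per patient.** The power statement expects procedure times of 1.5–4.5 h, so D is at most about 3 h. One excluded LMA patient of 44 then moves the estimate by at most 3 × 60 / 44 = 4.1 minutes, and two by about 8. Expected numbers converted are 0.02 × 44 = 0.9 and 0.05 × 44 = 2.2.

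**6. The opposite risk.** Suppose the difference in unconverted patients is exactly 0.5 h and converted patients have ETT-like times (D = -0.5 h). Analysing all randomised patients then declares non-inferiority in 5.5% (c = 2%) or 6.5% (c = 5%) of trials, against 4.9–5.0% in the unconverted set. Neither set tells the whole story alone.

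**The case against.** **The exclusion is inferred.** Item 8 answers an ethics-form prompt about participants leaving the study and is not an analysis-set rule. The form asks separately about withdrawal of data, and procedure time is a same-day chart value that could still be analysed. A reader might infer that the plan orders converted patients' data to be discarded; it does not say so. What remains is the contrast with the Holter patients and the absence of any statement that keeps the data. The paragraph on LMA placement in Research Description, item 4, is also cut off in the available text, so the statement about absence is limited to what can be read.

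**The arm imbalance is thinly supported.** The rule covers both arms, incorrect placement is listed as a risk for both, and the imbalance rests on one entry in a risk list. This justifies probably mainly LMA and nothing firmer.

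**The bias may be small.** A reader might infer that the rule favours LMA, or that the bias could never be bounded. The documents support neither. The sign depends on D. REDCap randomisation would show how many patients were withdrawn from each arm, and the expected time range limits the shift per patient. High conversion rates have no support either. Eligibility points to low ones: the criteria exclude severe reflux and high aspiration risk, and add: "Patients will also be excluded if the attending anesthesiologist determines that they would not be suitable candidates for intubation with either method".

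**The unconverted set has a claim of its own.** The hypothesis can be read as anesthesia actually delivered by LMA, and step 6 shows that all-randomised analysis can dilute a true difference. This stands, and is why both sets should be reported. It does not justify removing converted patients from the study.

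**Conclusion.** The point holds as a defect in the handling of converted patients. Followed as written, the plan most naturally produces a post-randomisation exclusion related to the assigned airway, in a trial with no defined analysis set. The direction and size of the resulting bias are not identified.

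At the lower conversion rates that eligibility makes more plausible, the effect is modest across most of the assumed time effects. The one-sided 5% error reaches 8–10% only at 5% conversion with converted cases running 1 to 1.5 h longer. These figures rest on an inferred alpha, assumed conversion rates and time effects, and conversion in the LMA arm only. The per-patient limit of about 4 minutes rests on the plan's expected range of procedure times, which is not a guaranteed bound.

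The case for changing the sentence does not depend on a large bias: retention is cheap, and outcomes not collected after withdrawal may not be recoverable.

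**What to change.** Replace the conversion sentence in item 8 with text to this effect: patients converted from the assigned airway stay in the study, have all outcomes collected including the satisfaction survey, and are analysed in the arm to which they were randomised; conversion is reported by arm. Limit withdrawal to participants who ask to be removed.

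Report the unconverted (per-protocol) set alongside and discuss any disagreement. Whether non-inferiority must hold in both sets is the sponsor's choice and should be stated in advance.

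The cost is a short amendment. Chart-based outcomes need no new collection, but the survey must still be given to converted patients. Some power is lost if conversion lengthens procedures. With 44 per arm, one-sided 5% and no difference in unconverted patients, simulated power goes from 0.82 (unconverted only) to 0.79 (all randomised) at 5% conversion and +0.5 h. At 2% and +0.25 h it is 0.82 in both. Clinical handling of conversion is unchanged.
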